9.2.3 Exclusion Criteria

Patients will be excluded from the study sample if they have any of the following:

- ≥ 1 written prescription, medication administration or medication history record for linagliptin or other DPP-4 inhibitor in the EHR data during the 180-day pre-index period (medication codes for DPP-4 inhibitors in Table 2 of [Annex 1, Appendix B](#))
- ≥ 1 written prescription or medication administration for a new antihyperglycemic medication other than linagliptin on the index date

New antihyperglycemic medication will be defined as a written prescription or medication administration for any antihyperglycemic medication that was not present in the patient's written prescription, medication administration, or medication history records during the 180-day pre-index period. Medication codes for antihyperglycemic medications are shown in Tables 2 through 13 of [Annex 1, Appendix B](#). Individual antihyperglycemic medications will be distinguished by generic name using the column labelled "Medication Name" in Tables 2 through 13. Combination products containing two generic ingredients will be considered as two distinct antihyperglycemic medications.

Note: This exclusion criterion is designed to exclude patients from the study sample if they start a new antihyperglycemic medication other than linagliptin on the index date. Patients that start a new antihyperglycemic medication in the follow-up period will not be removed from the study sample to avoid creating a biased sample. Addition of a new antihyperglycemic medication during follow-up will be evaluated through the sensitivity analysis described in Section 9.7.4.4. While we will be capturing additions of new therapies, discontinuation of linagliptin is not able to be accurately measured in electronic record data. The electronic record data capture prescriptions written by a prescriber, but it is not possible to know if patients received and adhered to their medication and there are no structured data fields to identify if and when a medication was discontinued by the patient or the provider.

- ≥ 1 diagnosis code or procedure code representing renal transplant, solid organ transplant, or bone marrow transplant in the EHR data during the 180-day pre-index period or on the index date (diagnosis and procedure codes in [Annex 1, Appendix A](#))
- ≥ 1 diagnosis code representing malignancy in the EHR data during the 180-day pre-index period or on the index date (diagnosis codes in Annex 1, Appendix A)

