7. RATIONALE AND BACKGROUND

Patients with type 2 diabetes mellitus (T2DM) have progressive decline in renal function and this decline in function is greater than age-related decline in patients without diabetes (1-4). Selection of glucose lowering agents is often affected by the level of renal function. Dipeptidyl peptidase-4 (DPP-4) inhibitors are approved to treat hyperglycemia among adults with T2DM with a wide range of renal function. In contrast to most other DPP-4 inhibitors (5), linagliptin does not require dose adjustment as renal function declines. Without further requirement of dose adjustment, linagliptin affords simplicity for chronic management of HbA1c.

Current literature indicate that decline in renal function is also associated with glycemic control, hypertension, albuminuria and dyslipidemia (9-11). However, there is limited evidence about the real world effectiveness and safety of linagliptin across different age and renal functions among adults with T2DM.

Data from clinical studies demonstrate that the expected reduction in HbA1c should be similar across the range of ages, but direct comparisons with younger patients are not available. Barnett et al reported on 238 patients aged 70 or older randomized to linagliptin 5 mg daily (n = 160) or placebo (n=78). The placebo adjusted mean difference in HbA1c after 24 weeks was -0.64% (95% CI -0.81 to -0.48) (12). Inzucchi et al reported on 247 patients aged 70 or older randomized to linagliptin (n = 126) or placebo (n = 121) added to basal insulin (13). The placebo adjusted mean difference in HbA1c after 24 weeks was -0.77 (94% CI -0.95 to -0.59). These values are consistent with other studies of linagliptin, but do not provide direct comparison data with younger patients.

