9.2 SETTING

9.2.1 Observation Period

This will be a non-interventional study using existing Optum EHR data for the period of July 1, 2011 through March 31, 2017. Patients with a written prescription for linagliptin will be identified during an identification period starting on January 1, 2012 and ending on September 30, 2016. The date of the first written prescription for linagliptin during the identification period will be designated as the index date without a prior prescription for linagliptin in the pre-index period.

Baseline characteristics will be evaluated during the 180-day period prior to the index date (pre-index period) and on the index date. Outcomes will be assessed during the 180-day period following the index date (follow-up period). A diagram of the study observation period is provided in Figure 1.

Figure 1. Study Observation Period

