9.2.2 Inclusion Criteria

To be included in the study sample, patients must meet all of the following criteria:

- ≥ 1 written prescription for linagliptin (Tradjenta[®], Jentaducto[®], or Jentaducto XR[®]) in the EHR data during the identification period (medication codes for index medications in Table 1 of [Annex 1, Appendix B](#))
- ≥ 40 years of age based on the year of the index date
- First active date in the EHR is ≥ 180 days prior to the index date
- ≥ 1 diagnosis code representing T2DM in the EHR data during the 180-day pre-index period or on the index date (diagnosis codes in Annex 1, Appendix A)
- ≥ 1 HbA1c value during the 180-day pre-index period or on the index date
- ≥ 1 HbA1c value 60 to 180 days after the index date

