9.5 STUDY SIZE

This study is exploratory and not characterized with *a priori* hypotheses. All patients identified in the data that meet the inclusion criteria and do not meet the exclusion criteria will be included in the study population.

A sample size calculation was conducted to determine the minimum number of patients that would be required to detect a change in HbA1c of at least 0.5% among the cohort groups. Based on previously published studies, it was assumed that the standard deviation for the 24-

week mean change in HbA1c from baseline could range between 1.2 (based on the placebo adjusted value in the MARLINA-T2D trial (20)) and 1.5 (based on retrospective studies of diabetes treatments using electronic medical record data from across the United States (21)). Assuming a SD of 1.2 for the change in HbA1c, at least 92 patients would be needed in each of the two smallest groups of the cohort of interest (e.g., age, renal function, age by renal function) in order to have 80% power to detect a mean difference in HbA1c of at least 0.5% using a two-sided test at an alpha of 0.05. If the standard deviation for the change in HbA1c is 1.5, then 143 patients would be needed in each of the two smallest groups.

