Fourth, in contrast to many real world evidence studies, this study does not have an active comparator. Since all other DPP4 inhibitors require dose adjustment for declining renal function, a comparator study to show similar/different effectiveness would be difficult to design to be able to account for all the patient factors that contribute to medication distribution, elimination and dosing and likely would require an inordinately large data base.

Fifth, due to the descriptive nature of this study, multiple different comparisons are being conducted to evaluate change in HbA1c by age, renal function, and race categories. We have not adjusted our p values for multiplicity but we may perform post hoc adjustments if requested by reviewers during the publication process.

Finally, the findings from this study are expected to have limitations that are common to analyses conducted with retrospective EHR data. The possibility of misclassification exists in all studies that rely on retrospective data. Evidence of conditions and events that are based on reported diagnosis codes or procedure codes may not reflect confirmed diagnoses. While EHR data capture prescriptions written by a prescriber, it is not possible to know if patients received and adhered to their medication and there are no structured data fields to identify if and when a medication was discontinued by the patient or the provider. The EHR database does not include the entire medical chart for the patient, which raises the possibility of missing data. Unlike claims data, EHR data do not contain eligibility information and continuous eligibility is not able to be assessed. Services provided to the patient by facilities and providers outside of the healthcare systems providing EHR data to Optum will not be captured although this is not expected to be a major limitation in this study because the primary outcome, HbA1c, is likely to be measured by the same provider who wrote the patient's prescription for linagliptin. However, there may be circumstances where a patient may receive care that falls outside of their provider's electronic record system such as being treated at an out of network hospital.

Despite these limitations, EHR data are a powerful source of data for the examination of health outcomes in the "real world" setting away from the highly controlled environment of

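### The DPP-4 inhibitor exclusion looks back only 180 days and omits the index date, so some within-class switchers may enter as new initiators; flag them and repeat the analyses without them

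*Combined protocol and SAP*

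**What the plan says.** - **Prior use (Section 9.2.3).** The first exclusion applies to a written prescription, an administration or a "medication history record for linagliptin or other DPP-4 inhibitor in the EHR data during the 180-day pre-index period". Section 9.2.1 treats the index date as separate from this period. The transplant and malignancy exclusions name the index date as well; the DPP-4 inhibitor exclusion does not.
- **New drugs on the index date (Section 9.2.3).** The second exclusion covers other newly started antihyperglycemic drugs on that day, but only through prescriptions and administrations. A medication history entry made that day does not count. Section 9.2.4 allows this second exclusion to be dropped if it costs too many patients.
- **Available history.** Section 9.2.2 sets a minimum: "First active date in the EHR is ≥ 180 days prior to the index date". Section 9.2.1 uses "existing Optum EHR data for the period of July 1, 2011 through March 31, 2017", with index dates from January 1, 2012 to September 30, 2016.
- **No stop dates (Section 9.9, also 9.2.3).** The source captures prescriptions written, and "there are no structured data fields to identify if and when a medication was discontinued by the patient or the provider".
- **Renal rationale.** Section 7 says "linagliptin does not require dose adjustment as renal function declines", in contrast to most other drugs of the class. Section 9.9 goes further: "Since all other DPP4 inhibitors require dose adjustment for declining renal function".
- **Adjustment (Section 9.7.3).** The model includes pre-index HbA1c but no prior or background antihyperglycemic therapy. No analysis with a longer washout appears. The sensitivity analysis that Section 9.2.3 refers to concerns drugs added during follow-up.

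**The concern.** A DPP-4 inhibitor prescribed with refills more than 180 days before index may still be in use at index without a new record inside the window. Separately, the old drug may be recorded only in the medication history taken on the day of the switch. Either patient passes the exclusion as written.

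For such a patient the pre-index HbA1c was measured on the same drug class, so little further change should be expected. If these patients are spread evenly, every group's mean change shrinks alike. If they are commoner in some groups, the comparison across groups is biased for a reason unrelated to age or renal function. Section 9.1 asks whether effectiveness is comparable across groups, and Section 9.7.3 reports unadjusted p-values, so a modest differential bias could be read as a real difference, or could offset one. The primary description and both secondary objectives are exposed.

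**Working it through.** **1. The plan's own figures.** Section 9.5 asks for "80% power to detect a mean difference in HbA1c of at least 0.5% using a two-sided test at an alpha of 0.05". With n = 2(1.960 + 0.842)² SD² / 0.5²:

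- SD 1.2: n = 90.4, rounded up to 91; the t-based solution is 91.4, rounded up to 92.
- SD 1.5: n = 141.3, rounded up to 142; the t-based solution is 142.2, rounded up to 143.

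The stated 92 and 143 per group reproduce and are not in dispute.

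**2. Unused history.** From July 1, 2011 there are 184 days of data before an index date of January 1, 2012, and 1,918 days before September 30, 2016. The exclusion uses 180 of them.

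**3. Can anything planned correct it?** The therapy flags in Section 9.3.3.2 include DPP-4 inhibitors other than linagliptin, but they read the pre-index period, which the exclusion has already cleared of such records. Even if the general rule in Section 9.3.3 adds the index date, the flag is descriptive only. Adjusting for pre-index HbA1c does not help: at the same starting value, a switcher is expected to change less than a true initiator.

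**4. Size of the dilution.** Let f be the excess share of unrecognised switchers in one group over the other, and e the HbA1c reduction in a true initiator. With zero change in switchers, the group mean moves toward zero by f × e. The documents give no value for f, so the values below are illustrative. For e, take the placebo-adjusted effects quoted in Section 7, 0.64 and 0.77.

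| f | e = 0.64 | e = 0.77 |
|---|---|---|
| 5% | 0.03 | 0.04 |
| 10% | 0.06 | 0.08 |
| 20% | 0.13 | 0.15 |
| 30% | 0.19 | 0.23 |

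An artefact as large as 0.5 points would need f = 0.5/0.64 = 78% or 0.5/0.77 = 65%.

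**5. Chance that the artefact alone gives p<0.05.** Section 9.7.1 gives more than 2,500 patients in the smallest age group and more than 3,000 in the oldest. With SD 1.5:

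SE = 1.5 × √(1/2,500 + 1/3,000) = 0.041, and 1.96 × SE = 0.080.

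The chance is approximately Φ(bias/SE − 1.96):

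- f = 10% (bias 0.064 to 0.077): 35% to 47%.
- Bias 0.08: about 50%.
- f = 20% (bias 0.128 to 0.154): 88% to 97%.

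The documents give no eGFR group sizes. For f = 20% and e = 0.64, the chance is about 11% at the minimum sizes (92 with SD 1.2, or 143 with SD 1.5). At an assumed 1,000 per group it is 67% (SD 1.2) or 48% (SD 1.5).

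**The case against.** A uniform 180-day washout is a defensible choice, and the exclusion has a real safeguard: it uses three record types. A hidden switcher must have no prescription, administration or medication history entry for a DPP-4 inhibitor in the whole window. Every patient also needs a T2DM code and an HbA1c in the pre-index period or on the index date, so most will have had recent contact. This narrows the gap. It does not close it, and it does not reach medication history recorded on the index date.

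Clustering at low eGFR is not shown. A need for dose adjustment explains a dose change as readily as a switch, and a dose change would normally leave a new prescription, which excludes the patient if it falls in the window. Sections 7 and 9.9 also differ on whether most or all other drugs of the class are affected, and no separate mechanism is given for age. Clustering stands as a plausible inference and no more.

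A reader might infer that a bias of 0.08 would by itself produce p<0.05. It would not: an expected shift of 1.96 standard errors reaches significance about half the time. That standard error comes from age groups, while the mechanism concerns eGFR. It also rests on feasibility counts that list no T2DM, transplant, malignancy or index-date drug criteria and accept any HbA1c in the six months after index.

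A reader might also infer that the exclusion should be replaced by one covering all history. The documents do not support that either. Eligibility would then depend on calendar time and record length, genuine former users would be lost, and Section 9.7.1 already warns of small eGFR cells.

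Finally, Section 9.12 concedes that the 180-day window may misclassify clinical characteristics, and Section 9.5 calls the study exploratory. Neither names prior DPP-4 inhibitor use.

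**Conclusion.** The gap is real on the text. Prior DPP-4 inhibitor use is screened only through records in the 180 days before index, the index date is not covered, stop dates do not exist, and no planned adjustment or sensitivity analysis addresses it. The direction in an affected group is toward a smaller HbA1c change. The size cannot be established. Under the stated assumptions it is 0.06 to 0.08 points for a 10-point excess share of switchers and 0.13 to 0.15 for a 20-point excess, well below the 0.5-point planning difference.

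These figures rest on an undocumented share, zero change in switchers, and placebo-adjusted effects from two trials in patients aged 70 or older, applied to an uncontrolled before-after change at all ages. They do not show that the low-eGFR results will be biased. They do show that, in groups of thousands, a modest imbalance could yield a nominally significant difference. This is a worthwhile, low-cost improvement and does not undermine the study.

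**What to change.** Keep the 180-day main sample, and make these changes:

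1. In Section 9.2.3, extend the exclusion to records on the index date for DPP-4 inhibitors other than linagliptin, including medication history. This would also hold if the second exclusion is relaxed under Section 9.2.4.
2. Flag any DPP-4 inhibitor record in all EHR data available before index.
3. Report the flag by age and eGFR group, which replaces an unknown share with a count of recorded earlier use.
4. As a sensitivity analysis, repeat the HbA1c change and goal-attainment tables and the OLS model without flagged patients.
5. Name the residual risk of unrecorded prior use in Section 9.9 or 9.12, and reconcile the statements in Sections 7 and 9.9 about most versus all other DPP-4 inhibitors.

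The cost is a little extra programming and output from data already held, and low-eGFR cells will be smaller in the sensitivity analysis. Look-back will vary from 184 to 1,918 days at most, and less where a patient's record starts later, so the flag adds almost nothing for patients indexed in early 2012. Flagged patients will include genuine former users, so the repeated analysis should be read beside the main one and not in its place.

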Limited data from studies evaluating linagliptin in patients with renal impairment suggest that glycemic control is maintained across different levels of renal function. Groop et al analyzed data from three 24 week linagliptin clinical trials (n = 2,262) in which data from 2,143 subjects were available to calculate renal function using the Modified Diet Renal Disease (MDRD) equation (14). Subjects were divided by renal function into normal renal function (eGFR \geq 90 ml/min/1.73 m²), mild renal impairment (eGFR 60 to < 90 ml/min/1.73 m²) and moderate renal impairment (eGFR 30 to < 60 ml/min/1.73m²). Distribution of subjects assigned to linagliptin vs. placebo by renal function category was as follows: 1) normal renal function: 870 linagliptin subjects and 342 placebo subjects; 2) mild renal function: 620 linagliptin subjects and 218 placebo subjects; and 3) moderate renal function: 68 linagliptin subjects and 25 placebo subjects. The reduction in HbA1c was consistent across ranges of renal function. However, the number of patients in the moderate renal dysfunction category was quite small, so there is greater uncertainty about the magnitude of the HbA1c reduction in this group. These observations support the current proposal to demonstrate comparable effects in glycemic effectiveness across the range of renal function categories and provide more information in patients with low renal function especially in patients with eGFR < 45 ml/min/1.73 m².

For better management of hyperglycemia it is pertinent to understand the glycemic effectiveness of linagliptin among adults with T2DM with varying age and renal function who are treated in the real world setting. With a potentially larger sample size, it is possible to compare the glycemic effectiveness of linagliptin across the range of ages and renal function.

The aim of the current study is to compare real world glycemic effectiveness across a range of ages and renal function among adults with T2DM who are initiated on linagliptin.

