- Pre-index renal function—Pre-index renal function will be assessed using estimated glomerular filtration rate (eGFR) which will be calculated using the Chronic Kidney Disease Epidemiology Collaboration (CKD-EPI) equation (18). This equation

requires variables for serum creatinine, age, sex, and race but weight and height are not required because the results are normalized to 1.73 m² body surface area (an accepted average adult surface area) (19). The last (most recent) serum creatinine value in the pre-index period (including the index date) will be used for the serum creatinine (Scr) variable. The CKD-EPI equation (18) to estimate GFR in units of ml/min/1.73m² after incorporating multiplication factors for race and sex into the intercept is displayed in [Table 2](#). For purposes of this eGFR calculation, race will be categorized as either AA or non-AA (includes White, Asian and Other/Unknown).

Table 2. CKD-EPI equation (Adapted from Reference 18)

Race	Sex	Scr (mg/dL)	Equation for eGFR in units of ml/min/1.73m ²
AA	Female	≤ 0.7	$eGFR = 166 \times \left(\frac{Scr}{0.7}\right)^{-0.329} \times (0.993)^{Age}$
AA	Female	> 0.7	$eGFR = 166 \times \left(\frac{Scr}{0.7}\right)^{-1.209} \times (0.993)^{Age}$
AA	Male	≤ 0.9	$eGFR = 163 \times \left(\frac{Scr}{0.9}\right)^{-0.411} \times (0.993)^{Age}$
AA	Male	> 0.9	$eGFR = 163 \times \left(\frac{Scr}{0.9}\right)^{-1.209} \times (0.993)^{Age}$
Non-AA	Female	≤ 0.7	$eGFR = 144 \times \left(\frac{Scr}{0.7}\right)^{-0.329} \times (0.993)^{Age}$
Non-AA	Female	> 0.7	$eGFR = 144 \times \left(\frac{Scr}{0.7}\right)^{-1.209} \times (0.993)^{Age}$
Non-AA	Male	≤ 0.9	$eGFR = 141 \times \left(\frac{Scr}{0.9}\right)^{-0.411} \times (0.993)^{Age}$
Non-AA	Male	>0.9	$GFR = 141 \times \left(\frac{Scr}{0.9}\right)^{-1.209} \times (0.993)^{Age}$

- Pre-index renal function categories—Patients will be categorized into one of the following renal function groups based on their eGFR during the pre-index period (including the index date):
 - < 30 ml/min/1.73m²
 - 30 to 44 ml/min/1.73m²
 - 45 to 59 ml/min/1.73m²
 - 60 to 89 ml/min/1.73m²
 - ≥ 90 ml/min/1.73m²
 - Not available

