9.9 LIMITATIONS OF THE RESEARCH METHODS

This study has several limitations inherent to its non-interventional study design. There may be baseline differences in the different age and renal function categories. In randomized clinical trials, these differences are mitigated by randomization. Among the important considerations is if there are substantial differences in baseline HbA1c. It is well known that the change from HbA1c is a function of baseline HbA1c, ie, the higher the baseline HbA1c, the greater the change from baseline even with comparable doses of the glucose lowering medication. This observation has been confirmed by Esposito et al (22) in their analyses of several DPP4 inhibitors.

Second, we have selected a follow up window of 6 months rather than a longer window e.g. up to 1 year. Maximal effectiveness is usually achieved by 6 months, although in randomized controlled trials HbA1c values may be lower at later time points. This limitation is balanced against the observation that medication persistence at 6 months will likely be

better than at 12 months and the fact that we wish to maximize the numbers of patients in each of the age and renal function cells.

Third, duration of T2DM is likely to be longer in patients with lower renal function. Increased duration of diabetes is also associated with greater reductions in beta cell function. Since one of the mechanisms of DPP4 inhibitor medications is to increase GLP-1 mediated insulin secretion, reduced renal function could theoretically be associated with diminished glycemic effectiveness. If the current study supports this observation, this will confound the claim of comparable glycemic effectiveness across the range of renal function, but it will be an important observation for the management of T2DM patients. Lajra et al reported on a retrospective analysis of 202 patients from two separate trials in which patients with > 10 years of diabetes were randomized to linagliptin 5 mg (n = 122) or placebo (n = 80)(15). The placebo adjusted mean difference in HbA1c was -0.66% (95% CI -0.85 to -0.38). No direct comparisons were made with shorter duration of diabetes. However, these data suggest that differences in duration of diabetes are unlikely to have a major effect on the data obtained in the current proposal.

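### Dialysis, red-cell transfusion and erythropoietin are neither excluded nor flagged, so the fixed HbA1c <7.0% goal may not be the same measure across renal groups

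*Combined protocol and SAP*

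**What the plan says.** **Exclusions.** Besides the two drug-history criteria, Section 9.2.3 removes patients with a "diagnosis code or procedure code representing renal transplant, solid organ transplant, or bone marrow transplant in the EHR data" and patients with a "diagnosis code representing malignancy in the EHR data during the 180-day pre-index period". Dialysis, transfusion and erythropoietin do not appear in the criteria, the covariates (9.3.3), the model list (9.7.3), the limitations (9.9) or the bias section (9.12).

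**Renal group.** Section 9.3.3.2 assigns the group from CKD-EPI eGFR: "The last (most recent) serum creatinine value in the pre-index period (including the index date) will be used for the serum creatinine (Scr) variable". The lowest category is <30 with no lower bound and no dialysis category. Patients without an eGFR go to a not-available group.

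**Goal attainment.** Under Section 9.3.2.2 a patient reaches goal with any HbA1c below 7.0% in days 60 to 180. Section 9.7.3 compares categorical measures across strata by chi-square. The multivariable model named there is for change in HbA1c only.

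**Emphasis.** Section 7 wants the study to "provide more information in patients with low renal function especially in patients with eGFR" below 45 ml/min/1.73m². That covers both the <30 and the 30 to 44 groups.

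**Limitations.** Section 9.9 says "There may be baseline differences in the different age and renal function categories" and goes on to baseline HbA1c and diabetes duration. It does not ask whether HbA1c and eGFR measure the same thing in every renal group.

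**The concern.** HbA1c depends on red-cell lifespan as well as on glucose. If dialysis, transfusion or erythropoietin makes it read low, patients above the goal on a valid measure can be counted as reaching it. Because any value in the window counts, one transiently low reading is enough, even if the last value is higher.

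If these patients cluster in eGFR <30, attainment there is raised for a reason unrelated to linagliptin. Section 9.9 itself raises the possibility that effectiveness is lower with reduced renal function. A low-reading HbA1c would help to hide such a loss, and so would favour the comparable-effectiveness conclusion named in Sections 7 and 9.1. If there were no true difference, it would create a spurious advantage for the lowest group.

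**Working it through.** **1. The plan's own figures (Section 9.5).** The inputs are "80% power to detect a mean difference in HbA1c of at least 0.5% using a two-sided test at an alpha of 0.05". With n per group = 2 × [SD × (1.960 + 0.842) / 0.5]²:
- SD 1.2 gives 90.4, rounded up to 91. The t-test version gives 91.4, rounded up to 92.
- SD 1.5 gives 141.3, rounded up to 142. The t-test version gives 142.2, rounded up to 143.

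The plan's 92 and 143 reproduce and are not in question.

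**2. Where these patients would fall.** Solving the plan's Table 2 equation for creatinine at eGFR 30 gives Scr = κ × [30 / (k × 0.993^age)]^(−1/1.209), where k is the table's constant and κ is 0.7 (female) or 0.9 (male). For ages 45 to 75 across the four sex and race rows this is about 1.7 to 2.8 mg/dL. Most patients with kidney failure would therefore be expected in <30, but no rule puts them there. Transfused or erythropoietin-treated patients can fall in any group.

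**3. Effect on goal attainment (assumptions).** The documents give no follow-up HbA1c distribution, no share affected and no size of error. Assumed ranges:
- follow-up mean m of 7.5 to 8.0
- SD s of 1.2 to 1.5, borrowed from the plan's SDs for change because none is given for the level
- share affected f of 10% to 50% of eGFR <30
- low reading b of 0.25 to 1.0 points
- one normally distributed value per patient, and no true difference between renal groups

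Attainment without error: p0 = Φ((7.0 − m)/s). With error: p1 = (1 − f) × p0 + f × Φ((7.0 − m + b)/s).

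Middle case (m = 7.5, s = 1.2, f = 0.30, b = 0.5): p0 = Φ(−0.417) = 33.8%. Among affected patients Φ(0) = 50%. The group shift is 0.30 × (50 − 33.8), which without rounding is 4.8 points, so p1 = 38.7%.

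| m, s | p0 | f 10%, b 0.25 | f 30%, b 0.5 | f 50%, b 1.0 |
|---|---|---|---|---|
| 7.5, 1.2 | 33.8% | +0.8 | +4.8 | +16.2 |
| 7.5, 1.5 | 36.9% | +0.6 | +3.9 | +13.1 |
| 8.0, 1.2 | 20.2% | +0.6 | +4.1 | +14.9 |
| 8.0, 1.5 | 25.2% | +0.6 | +3.5 | +12.4 |

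(Shifts in percentage points.)

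**4. Would it be declared a difference?** The two-sided 5% comparison of 33.8% with 38.7% rejects with probability Φ([d√n − 1.96 × √(2p̄(1−p̄))] / √(p0(1−p0) + p1(1−p1))), where d = p1 − p0 and p̄ is their mean. This gives about 13% with 143 per group and about 62% with 1,000 per group. Section 9.7.1 gives no count for eGFR <30, so the relevant n is unknown.

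**5. Effect on change in HbA1c.** An error of the same size at baseline and follow-up subtracts out. Only a change of state between the two matters. If 10% of the group started such treatment after baseline and read 0.5 points low (both assumed), the mean change would shift by 0.10 × 0.5 = 0.05 points, one tenth of the 0.5 points in Section 9.5.

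**The case against.** The strongest reply is that the premise comes from outside the plan. No section says HbA1c or CKD-EPI is unreliable in these patients, and direction, size and prevalence cannot be derived from the text. That stands, so everything in step 3 of the working is illustration. A reader might take a single SD of 1.2 and 20% to 40% affected, with m = 7.5 and b = 0.5, and read 3.2 to 6.5 points as an estimate. With SD 1.5 the same inputs give 2.6 to 5.2, and the full range is far wider.

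A reader might also infer that all these patients sit in eGFR <30. Section 9.3.3.2 does not support this, since placement depends on one creatinine value and some patients have none.

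The primary outcome is largely protected, and Section 9.5 calls the study exploratory. Both points stand, and they limit the matter mainly to a secondary outcome. Comparing that outcome across renal groups is nevertheless a stated objective.

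The plan has partial cover. The change model includes pre-index HbA1c, the Quan-Charlson score and common comorbidities, and Sections 9.9 and 9.12 acknowledge misclassification in general terms. None of this reaches the unadjusted goal comparison. Section 9.2.3 also points to a Section 9.7.4.4 and Section 12 to table shells in an analysis plan; neither can be seen here. As described, 9.7.4.4 concerns new antihyperglycemic drugs during follow-up, not this.

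Finally, removing patients for events after the index date, and resting the conclusion on those who remain, could itself bias the comparison. Section 9.2.3 keeps patients who start new drugs in follow-up for that reason. This objection stands and shapes the fix.

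**Conclusion.** The omission is confirmed by the text: these patients are not excluded, flagged or discussed, the lowest renal group is open-ended, and a fixed threshold is compared across renal groups without adjustment. The consequence is a risk of unknown size. If HbA1c reads low in part of eGFR <30, attainment there is inflated by about 0.6 to 16 points over the assumed ranges, and by about 5 points at mean 7.5, SD 1.2, a 0.5-point error and 30% affected. At 10% affected and a 0.25-point error it is under 1 point.

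A reader might go further and conclude that the goal comparison is shown to be invalid, or that the primary result is biased. The documents support neither: they give no prevalence or error size, and a stable error largely cancels in the change. The point is a cheap improvement to the renal comparison of goal attainment. It does not call the sample-size figures or the main cohort into question.

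**What to change.** - Create a flag for any dialysis, red-cell transfusion or erythropoietin record in the 180-day pre-index period or on the index date, and report its frequency by eGFR group, including the not-available group.
- Pre-specify a sensitivity analysis that repeats the renal-group comparisons of goal attainment and change in HbA1c without flagged patients, reported beside the main result and not in place of it.
- Tabulate new records of this kind during follow-up by eGFR group, descriptively, and keep those patients in the main analysis.
- State in Sections 9.9 and 9.12 that the validity of HbA1c and eGFR may differ across renal groups. If the two results differ, qualify any comparability statement on goal attainment for eGFR <30.

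This follows the approach in Section 9.2.4 of flagging patients for subanalysis. The cost is one code list and a repeat of existing tables in the same database. There are two drawbacks. The sensitivity analysis has fewer eGFR <30 patients, by a number that cannot be computed because Section 9.7.1 gives no count for that group. The flag will also miss services at outside facilities, which Section 9.9 says are not captured. If the flag proves rare, the frequency table would suggest a small effect, subject to that incomplete capture.
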